1. OBJECTIVES

The objective of this single center paired cohort study is to evaluate the diagnostic accuracy of EUS-FNA with ROSE compared to EUS-FNB without ROSE. If EUS-FNB without ROSE is shown to be non-inferior to the current standard of care of EUS-FNA with ROSE in pancreatic lesions, this study has the potential to make EUS-guided tissue acquisition more economical (with elimination for the need for cytopathology staff onsite) as well as provide core histological specimen without sacrificing the overall diagnostic yield.

1.1 STUDY DESIGN

Multicenter, Prospective, Single Blind, Randomized clinical trial. Patients will be randomly allocated (Using computerized software) with a 1:1 ratio either to the EUS-FNA with ROSE or FNB first group.

1.2 Primary Objectives

To compare the diagnostic accuracy of fine-needle biopsy (FNB) sampling without rapid onsite evaluation (ROSE) with the fine needle aspiration (FNA) with ROSE in pancreatic mass lesions

1.3 Secondary Objectives

To compare:

Specimen adequacy Percentage of histology cores obtained Number of passes Rate of technical failures Adverse events

2. BACKGROUND AND RATIONALE

2.1 Background

Endoscopic ultrasound (EUS) guided fine needle aspiration (EUS-FNA) is the primary technique for tissue acquisition for pancreatic lesions. Despite widespread adoption of the techniques, the diagnostic yield of EUS-FNA for pancreatic lesion is highly variable, with sensitivities ranging from 64-95%, specificities ranging from 75-100% and overall diagnostic accuracy ranging from 78-95%.

Despite its mainstay as the primary technique for tissue acquisition, EUS-FNA has several limitations. The standard EUS-FNA does not routinely provide core biopsy specimen with preserved tissue architecture, which is required for immunohistochemical staining and for definitive diagnosis of conditions, such as lymphoma, gastrointestinal stromal tumors, IgG-4-associated lymphoplasmacytic sclerosing pancreatitis. Furthermore, the diagnostic yield of EUS-FNA is highly dependent on the availability of bedside cytotechnologist or cytopathologist for rapid onsite evaluation (ROSE), which increases the overall cost required to perform EUS-FNA.

Recently, multiple dedicated EUS fine needle biopsy (FNB) needles have been developed to obtain core specimens. Early small studies have shown promising results with these EUS-FNB needles (1-6).

The objective of this single center paired cohort study is to evaluate the diagnostic accuracy of EUS-FNA with ROSE compared to EUS-FNA with ROSE. If EUS-FNB

without ROSE is shown to be non-inferior to the current standard of care of EUS-FNA with ROSE in pancreatic lesions, this study has the potential to make EUS-guided tissue acquisition more economical (with elimination for the need for cytopathology staff onsite) as well as provide core histological specimen without sacrificing the overall diagnostic yield.

2.2 RATIONALE

The rationale for this study is as follows:

The objective of this single center paired cohort study is to evaluate the diagnostic accuracy of EUS-FNA with ROSE compared to EUS-FNA with ROSE. If EUS-FNB without ROSE is shown to be non-inferior to the current standard of care of EUS-FNA with ROSE in pancreatic lesions, this study has the potential to make EUS-guided tissue acquisition more economical (with elimination for the need for cytopathology staff onsite) as well as provide core histological specimen without sacrificing the overall diagnostic yield.

2.3 PARTICIPANT SELECTION

Eligibility Criteria

Inclusion Criteria for Participants

Patient \geq 18 years of age referred for EUS-guided biopsy for pancreatic mass lesions

Exclusion Criteria

Refusal to consent form Uncorrectable coagulopathy (INR > 1.5) Uncorrectable thrombocytopenia (platelet < 50,000) Uncooperative patients Pregnant women (women of childbearing age will undergo urine pregnancy testing, which is routine for all endoscopic procedures) Medically unstable for sedation Entirely cystic lesions Lesions inaccessible to EUS

Inclusion of Women, Minorities and Other Underrepresented Populations This protocol is open to males and females of all races.

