7. PROCEDURE PLAN

All EUS/FNB and EUS/FNA will be performed using a linear array echoendoscope by one of seven experienced EUS physicians at JHH. All patients will undergo both EUS/FNB and EUS/FNA. Patients will be randomized to either FNB or FNA first by

means of computer-generated numbers. The endoscopist will not be blinded to the randomization; however, the study pathologist will be blinded to randomization.

EUS/FNB will be performed using similar techniques for tissue acquisition as FNA using 22-g FNB needle (Medtronic SharkCore or Boston Scientific Acquire). Lesions will be identified using EUS and punctured with the 22-g FNB needle (10-15 back and forth movements per needle pass, fanning as appropriate). After the lesion is punctured, the stylet will be removed and 10cc suction will be applied. FNB samples will be placed directly into formalin containers and sent to be processed by surgical pathology.

EUS/FNA with ROSE will be performed using standard techniques via 22-g FNA needle (Cook Medical EchoTip Ultra or Boston Scientific Expect or Medtronic Beacon). Lesions will be identified using EUS and punctured with the FNA needle (10-15 back and forth movements per needle pass, fanning as appropriate). After the lesion is punctured, the stylet will be removed and 10cc suction will be applied. FNA specimens will be processed for ROSE using standard techniques with bedside smear slide evaluation and liquid-based cytology and cell-block preparation.

The first randomization assigned EUS sampling technique will be used until adequate specimen is achieved (up to 3 passes total). After 3 passes, the patient will undergo the other EUS sampling technique until adequate specimen is achieved (up to 3 passes total). If inadequate biopsies are obtained after a total of 6 passes (3 with initial tissue acquisition techniques, 3 with the other technique), the endosonographer will be permitted to utilize any EUS sampling technique preferred to obtain a diagnosis during the same procedure or at a later date.

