8. PATIENT FOLLOW-UP

All patients will recover from their procedures according to standard practice. They will remain NPO the night after the procedure. After finishing the procedure, all patients will be carefully monitored per standard protocol in the recovery room and be discharged when fully awake and pain-free. Patients will be contacted by telephone at 24-48 hours to ascertain and document any early adverse events that may have arisen. Long-term clinical follow up will be based on clinical indications.

To determine the safety of procedure, all pre, intra- and immediate post-procedure adverse events will be recorded and rated according to ASGE lexicon (7) for adverse events. Inpatients will be evaluated by study coordinator/PI on a daily basis during their hospitalization. Potential complications will be explained for patients at their discharge time and will be advised to refer whenever they have problems.

- a. Study duration and number of study visits required of research participants. Study duration: 2 years Number of subjects: 132 Follow-up visits: 0
- Blinding, including justification for blinding or not blinding the trial, if applicable.
 Due to the nature of study, treatment team will be aware of patient's group and it is not possible to make it double blinded. However, the study pathologist will be blinded to randomization.

- Justification of why participants will not receive routine care or will have current therapy stopped.
 Routine care will be followed
- d. Justification for inclusion of a placebo or non-treatment group. N/A
- e. Definition of treatment failure or participant removal criteria. The first randomization assigned EUS sampling technique will be used until adequate specimen is achieved (up to 3 passes total). After 3 passes, the patient will undergo the other EUS sampling technique until adequate specimen is achieved (up to 3 passes total). If inadequate biopsies are obtained after a total of 6 passes (3 with initial tissue acquisition techniques, 3 with the other technique), the endosongrapher will be permitted to utilize any EUS sampling technique preferred to obtain a diagnosis during the same procedure or at a later date.
- f. Description of what happens to participants receiving therapy when study ends or if a participant's participation in the study ends prematurely. No change in medical care will be expected.

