12. STATISTICAL CONSIDERATIONS

Overview: This study is designed as a non-inferiority trial.

Considering a success rate of 85% in the FNA with ROSE group, based published studies, we selected a non-inferiority margin (∂) of 10%, in accordance with the USFDA recommendations (8). Based on the following formula (9):

n = f(α, β) × [πs × (100 – πs) + πe × (100 – πe)] / (πs – πe – d)2

where πs and πe are the true percent 'success' in the standard and experimental treatment group respectively, and

 $f(\alpha, \beta) = [\Phi - 1(\alpha) + \Phi - 1(\beta)]2$

 Φ -1 is the cumulative distribution function of a standardized normal deviate

We calculated that our trial will require enrolling 120 patients for power of 80% and two sided α of 0.05.

Taking into consideration a 10% dropout rate, the total patients to be enrolled=132

Baseline demographics, pre-, intra- and post-intervention data will be prospectively collected on data collection forms which will be maintained in an electronic database system. Results will be reported as mean ± standard deviation (SD) for quantitative variables and percentages for categorical variables. The groups will be compared using the Student's t- test or Wilcoxon rank sum test for continuous variables and the chi-square test (or Fisher's exact test if required) for categorical variables. To compare

diagnostic accuracy between two EUS sampling techniques, we will use McNemar's test. Statistical significance will be based on two-sided design-based tests evaluated at α = 0.05. All statistical analyses will be performed using STATA.

a. Endpoints:

Primary:

Diagnostic accuracy will be defined as (true positive + true negative)/all samples. The final diagnosis will be based on one of the following criteria: (i) surgical pathology specimen from patients who underwent surgical resection; (ii) cytological or histopathological diagnosis of malignancy in patients with unresectable disease with appropriate imaging and clinical course of disease; (iii) cytological and histopathological diagnosis of benign disease with an appropriate clinical course of disease for minimum of 6 months.

Secondary:

1. Specimen adequacy

This will be defined as the proportion of samples in which a final histopathological diagnosis could be made.

2. Percentage of histology cores obtained

This will be defined as the proportion of samples in which a visible histology core biopsy was obtained

- 3. Number of passes Number of passes required for diagnosis

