- 4. Rate of technical failures

Technical failure was defined as the inability to perform the procedure, including the need to change the needle

5. Adverse events

All pre, intra- and immediate post-procedure adverse events will be recorded and rated according to ASGE lexicon for adverse events.

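### Attempts that yield no sample fall out of the primary accuracy comparison, and the EUS-access exclusion is not closed off before the sampling order is known

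*Combined protocol and SAP*

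**What the plan says.** Section 12 gives the primary endpoint as "Diagnostic accuracy will be defined as (true positive + true negative)/all samples" and compares the two techniques with McNemar's test. Its fourth secondary endpoint reads "Technical failure was defined as the inability to perform the procedure, including the need to change the needle". No analysis set is defined.

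Section 2.3 lists "Lesions inaccessible to EUS" among the exclusions. It does not define inaccessibility or say when, or by whom, it is judged.

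Section 7 states "All patients will undergo both EUS/FNB and EUS/FNA", so only the order is randomised, and adds "The endoscopist will not be blinded to the randomization". The pathologist is blinded. The same section describes finding the lesion as part of the study procedure: "Lesions will be identified using EUS and punctured with the 22-g FNB needle". Section 1.1 says "Patients will be randomly allocated (Using computerized software) with a 1:1 ratio" but does not place the allocation before or after the lesion has been seen.

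Section 8, item e, is headed "Definition of treatment failure or participant removal criteria". Its text covers only the limit of three passes per technique, the move to the other technique, and free choice of technique after six passes. It has no rule for a patient found ineligible after randomisation.

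**The concern.** A technique that cannot deliver a sample has failed as a diagnostic procedure. Under the literal primary definition that failure costs it nothing: there is no sample, so nothing enters the denominator. McNemar's test needs a result from both techniques, so the patient also drops out of the paired comparison unless a rule supplies the missing result, and there is none. The failure then shows only in a secondary endpoint.

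The exclusion adds a second way out. If inaccessibility is declared after the order is known, the whole patient can leave the study, and the event need not appear even as a technical failure. The allowance for dropout (132 enrolled for 120 needed, so 12 patients) does not say what counts as dropout and could absorb such removals.

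At stake is the non-inferiority conclusion. If FNB fails to give a sample more often than FNA, dropping those attempts hides part of a real disadvantage. If FNA fails more often, dropping them works against FNB.

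**Working it through.** No figure in the plan is in dispute. The check sets the rules side by side and then gauges how sensitive the comparison is.

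**The rules together**

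- Specimen obtained but inadequate: sections 7 and 8 keep the patient in and move on to the other technique. Section 12 defines adequacy as a proportion of samples, so a non-diagnostic specimen is still a sample and stays in the primary denominator.
- No specimen because the technique could not be carried out: technical failure under secondary endpoint 4, but no sample, so not in the primary denominator and no pair for McNemar's test.
- Lesion judged inaccessible: excluded under section 2.3, with no time limit. Where the trouble is access or puncture, this can overlap with the previous case, and no section says which rule prevails.

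**Effect of the denominator rule**

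Inputs from section 12: 120 patients, a success rate of 85% for FNA with ROSE, a margin of 10 points. Assumed: both techniques are 85% accurate whenever a sample is obtained; no sample is obtained with FNB in 4 patients and with FNA in 1 other patient.

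- Failures dropped: 85% against 85%, difference 0.
- Failures counted as not correct: FNB (120 − 4) × 0.85 / 120 = 98.6 / 120 = 82.2%; FNA (120 − 1) × 0.85 / 120 = 101.15 / 120 = 84.3%. Difference (FNB minus FNA) −2.1 points.
- General form: shift = net excess of failures × 0.85 / 120. One net failure gives 0.71 points; three give 2.1; six give 4.25.

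The sign follows the technique that fails more often. Swapping the 4 and the 1 gives +2.1 points.

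**Effect of removing whole patients**

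This is the route through the exclusion. Assumed: FNA 85% and FNB 75%, so the true difference sits at the margin; 15% of pairs FNA-correct/FNB-incorrect and 5% the reverse. Of 120 patients, 102 are then correct by FNA and 90 by FNB. Removing k pairs in which only FNA was correct gives a difference (FNA minus FNB) of (102 − k − 90) / (120 − k):

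- k = 0: 12/120 = 10.0 points
- k = 1: 11/119 = 9.2
- k = 3: 9/117 = 7.7
- k = 5: 7/115 = 6.1

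A simulation of 400,000 trials under the same assumptions declared non-inferiority when d + 1.96 × SE < 0.10. Here d is FNA minus FNB and SE = √(b + c − (b − c)²/n) / n, where b and c are the two discordant counts and n the pairs kept.

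| Share of FNA-correct/FNB-incorrect pairs removed | Mean patients removed | False non-inferiority |
|---|---|---|
| 0% | 0 | 3.3% |
| 5% | 0.9 | 4.5% |
| 10% | 1.8 | 6.5% |
| 20% | 3.6 | 12.6% |
| 30% | 5.4 | 22.7% |

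These figures take the unfavourable direction on purpose, and the interval rule is also an assumption. They show sensitivity to a few selective removals, not an expected bias.

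**The case against.** The strongest defence is the paired design. Both techniques use a linear echoendoscope and 22-gauge needles in the same patient, so access by EUS belongs mainly to the lesion, and excluding a patient removes both results. That stands: a lesion that neither needle can reach creates no difference between the techniques. It does not cover failure of one needle only. Section 7 names different needle models for the two techniques, and the technical-failure definition itself includes a needle change.

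Several stronger readings are tempting, and the documents do not support them:

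- A reader might infer that inaccessibility can be judged only once EUS has begun. Section 2.3 is silent on timing and does not rule out a judgement before the procedure, or at EUS before puncture. Nor does it name who decides; the endoscopist's role is an inference from the setting.
- A reader might infer that one event necessarily meets both rules. The exclusion speaks of access by EUS, the failure endpoint of carrying out the procedure and changing the needle. They can overlap at the boundary, no more.
- A reader might infer that any failed sampling can be relabelled as ineligible. Inadequate sampling has its own path in sections 7 and 8, which keeps the patient in.
- A reader might infer that the gap favours FNB. That needs more dropped failures with FNB than with FNA, and the documents give no rates.

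It is also fair to say that the 4-against-1 illustration measures the denominator rule, not the exclusion, and that the denominator problem would exist without the exclusion.

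**Conclusion.** The concern holds, with the primary denominator as the main defect and the undated exclusion as a contributing one. As written, an attempt that cannot be performed or gives no sample does not count against its technique in the primary analysis. Nothing prevents the access exclusion being applied after the order is known, by someone who is not blinded to it.

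Bias requires that the missing sample or the removal depends on which needle failed, and its direction follows the technique that fails more often. Its size cannot be estimated from the documents. With 85% accuracy and 120 patients, it is about 0.7 points per net dropped failure, so one to six would shift the difference by about 0.7 to 4.3 points against a margin of 10. Taken alone, the timing of the exclusion is close to a missing detail. It deserves correction because it sits beside a stated denominator rule that can bias the primary comparison.

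**What to change.** 1. In section 12, define the primary denominator as randomised patients with a final diagnosis, with one result per technique per patient. Count an attempt that cannot be performed or yields no sample as not correct, in both the accuracy figures and the paired comparison. Report how many randomised patients have no final diagnosis, since a patient with no tissue from either technique could still be lost there.
2. In sections 2.3 and 7, require accessibility on EUS to be recorded before the sampling order is randomised or revealed. Allow no exclusion for inaccessibility after that point, and report every post-randomisation exclusion by order and technique.
3. Reconcile the exclusion in section 2.3 with the technical-failure definition in section 12, so that each event falls under one rule. What counts clinically as accessible is for the investigators to define.

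The cost is a wording change, opening the allocation in the procedure room, and accuracy figures that may be slightly lower. No extra patients or procedures are needed.

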3. MULTICENTER GUIDELINES

Protocol Chair

The Protocol Chair is responsible for performing the following tasks:

- Coordinating, developing, submitting, and obtaining approval for the protocol as well as its subsequent amendments
- Assuring that all participating institutions are using the correct version of the protocol.
- Taking responsibility for the overall conduct of the study at all participating institutions and for monitoring the progress of the study.
- Reviewing and ensuring reporting of Serious Adverse Events (SAE)
- Reviewing data from all sites

Coordinating Center

The Coordinating Center is responsible for performing the following tasks:

- Ensuring that IRB approval has been obtained at each participating site prior to the first patient registration at that site, and maintaining copies of IRB approvals from each site.
- Managing central patient registration.
- Collecting and compiling data from each site.
- Establishing procedures for documentation, reporting, and submitting of AE's and SAE's to the Protocol Chair, and all applicable parties.
- Facilitating audits by securing selected source documents and research records from participating sites for audit, or by auditing at participating sites.

Participating Sites

Participating sites are responsible for performing the following tasks:

- Following the protocol as written, and the guidelines of Good Clinical Practice (GCP).
- Submitting data to the Coordinating Center.
- Providing sufficient experienced clinical and administrative staff and adequate facilities and equipment to conduct a collaborative trial according to the protocol.
- Maintaining regulatory binders on site and providing copies of all required documents to the Coordinating Center.
- Collecting and submitting data according to the schedule specified by the protocol.

4. QUALITY ASSURANCE

Authorized representatives of the Coordinating Center may visit participating sites to perform audits or inspections, including source data verification. The purpose of these audits or inspections is to systematically and independently examine all trial related activities and documents to determine whether these activities were conducted and data were recorded, analyzed, and accurately reported according to the protocol, Good Clinical Practice (GCP), and any applicable regulatory requirements.

5. DATA SUBMISSION

Data and/or completed case report forms must be transmitted by fax or e-mail to the Coordinating Center following the completion of each cycle as detailed in Section 16.1.1. Case report forms will be provided to participating sites by the Coordinating Center.

6. ADVERSE EVENT REPORTING

Definition of Adverse Event (AE)

An adverse event is the development of an undesirable medical condition or the deterioration of a pre-existing medical condition following or during exposure to a procedure done, whether or not considered causally related to the procedure. An undesirable medical condition can be symptoms (e.g., nausea, chest pain), signs (e.g., tachycardia, enlarged liver) or the abnormal results of an investigation (e.g., laboratory findings, electrocardiogram).

Definition of Serious Adverse Event (SAE)

A serious adverse event is an AE occurring during the procedure or any time after the procedure, that fulfills one or more of the following criteria:

- Results in death
- Is immediately life-threatening
- Requires in-patient hospitalization or prolongation of existing hospitalization
- Results in persistent or significant disability or incapacity
- Is a congenital abnormality or birth defect
- Is an important medical event that may jeopardize the patient or may require medical intervention to prevent one of the outcomes listed above

Protocol Chair

The Protocol Chair is ultimately responsible for the required reporting of all adverse events.

Coordinating Center

The Coordinating Center is the central location for the collection and maintenance of documentation of adverse events and is responsible for submitting adverse event reports to the Protocol Chair promptly. The Coordinating Center will maintain documentation of all adverse event reports for each participating site. Adverse event reports submitted to the Coordinating Center must be signed and dated by the participating site's Principal Investigator. The Coordinating Center will provide appropriate forms to be used by all participating sites for reporting adverse events. Information to be provided must include:

- Subject ID number, and initials
- Date of the event
- Description of the event
- Description of site's response to the event
- Assessment of the subject's condition
- Subject's status on the study (on study, off study, etc.)
- Attribution of event to study drug

Participating Sites

Participating sites are responsible for reporting adverse events to their IRB according to its specific requirements and to the Coordinating Center as follows:

Fatal Events whether anticipated or unanticipated, and whether or not related to the study must be reported to the Coordinating Center within 24 hours of the participating site Principal Investigator's learning of the event.

Serious and Unanticipated Adverse Events must be reported to the Coordinating Center within 24 hours of the participating site Principal Investigator's learning of the event.

Other Serious Adverse Events which may result in a change to the protocol, informed consent, or risk to subjects as specified in the protocol must be reported within three (3) working days of the participating site Principal Investigator's learning of the event.

Adverse Events which result in no change to protocol, informed consent, or risk to subjects must be reported to the Coordinating Center on a monthly basis.

All SAEs must be collected whether or not they are considered causally related to the investigational procedure. Investigators and other site personnel are responsible for reporting all casually related SAEs to their IRB and the Protocol Chair.

